7.2.3. EQ-5D-5L

EQ-5D-5L will be completed by participants at baseline, 4-week, 5 week and 10-week time points. There is likely to be a marked difference in quality of life once the boot/ plaster is removed, and so measurements will be made at both 4 weeks (with the boot/ plaster on) and 5 weeks (with the boot/ plaster usually off). We anticipate that measurement at 4 weeks will attribute to the restrictive nature of the boot/ plaster, whilst at 5 weeks will collect data on recovery/ healing. The EQ-5D-5L is a standardised descriptive system of health-related quality of life states consisting of five dimensions (mobility, self-care, usual activities, pain/discomfort, anxiety/depression) each of which can take one of five responses. It captures relevant issues e.g. walking, problems washing/dressing, as well as problems with usual activities including work and family/leisure activities, pain, and psychological impact¹⁵. It will be used to derive quality adjusted life years (QALYs).

7.2.4. Complications

Complications including; Blisters (presence and severity; minor/major), Pressure sores (presence and severity; grade 1-5), Failure of fixation (presence; medial/lateral/both), Operation/revision surgery, Wound breakdown, Wound infection (presence and severity; Minor (treatable with antibiotics/dressing) / major (needs surgical debridement), Compartment Syndrome, DVT (presence; below knee/above knee), Nerve Injury (presence; sensory/motor/both) and Pulmonary embolism occurring up to 12 weeks post-surgery will be recorded. Complications recorded will include those reported by patients, identified by the PI or delegated member of the research team during their routine clinical assessment and from their review of hospital records.

7.2.5. Return to usual activities

At baseline, patients will be asked for their employment status prior to injury (unemployed, homemaker, volunteer, full time education, part-time paid employment, full time paid employment). At 10 weeks participants will be asked for their current employment status and will be asked whether their ankle injury has an impact on every day activities (0 to 10 scale anchored by no effect on daily activities and completely prevented daily activities).

Absenteeism (days off work), presenteeism (feeling less productive at work), and time off usual social activities, are productivity losses that we will measure at 4 and 10 weeks, by questions included in the resource use questionnaire. Participants will also be asked if they drove pre-injury, whether they had started driving again, and the date they resumed driving.

7.3. Baseline Characteristics

7.3.1. Demographics and socioeconomics

Gender, age, marital status living situation, education level, employment status, driving status and pre-surgery height and weight/BMI will be collected at baseline.

7.3.2. Fracture characteristics

Characteristics of the fracture (classification, pattern) and a description of the hardware used during surgery will be recorded following a blinded review of radiographs performed by the Chief Investigator (see section 9.7 Radiographic Evaluation). Classification will be coded as Weber A, B or C, pattern will be coded as medial malleolar fracture or deltoid ligament injury .Fracture Complexity will be reported in the baseline CRF and will be coded as simple fibular fracture and comminuted fracture.

7.4. Resource Use

(i) Resources associated with administration of treatment in both arms (including materials used and time and grade of staff involved in fitting/removing the plaster/boot and providing the necessary instruction to patients) will be captured by the research team in the CRF at the 2 week post-surgery (baseline) and 6-week post-surgery (4 week post-randomisation) appointment in clinic.

(ii) Resources delivered by the treating hospital¹ at 10 weeks from randomisation will be collected from a review of patients' hospital notes at the end of the patient's participation. Data on inpatient admissions, outpatient appointments and outpatient therapies provided, as well as diagnostic tests performed will be collected onto CRF's by the research team from randomisation (2-week post-surgery) until last follow-up (12 weeks post-surgery). Date of event will be collected, to allow for costing the two different periods of resource use, in the two economic analyses.

¹ In this context, 'treating hospital' refers to the hospital in which the ankle fracture surgery is performed.

(iii) Participants' use of other health and social care resources, as well as informal care and loss of productivity, will be captured at the 4-week and 10-week time points via patient-completed questionnaires. Patient reported data will be collected from randomisation on:

- (a) Community-based health care services used. This will include contacts with GP doctor and nurses at the GP practice, at home or by telephone, and other health services required such as community physiotherapist and occupational therapist visits. Use of concomitant medications will also be patient reported.
- (b) Secondary care visits to hospitals
- (c) Use of social services, such as home help, food at home services and contacts with social worker.
- (d) Productivity losses, including a measurement of absenteeism and presenteeism, by adapting a few questions from the Work Productivity and Activity Impairment Questionnaire (WPAI): General Health Version 2.0¹⁶, a licence-free, well-known and validated questionnaire commonly used to measure productivity losses when patients take time-off work or are unproductive at work¹⁷⁻¹⁸. We will also collect losses in leisure time and informal care from friends and relatives.
- (e) Private expenses, such as travel, privately paid therapies or lost income.

The primary outcome is collected at 5 weeks post randomisation. Collection of resource use should follow the same time frame, so that costs and outcomes can be compared within the period. However, we feel strongly that the first resource use questionnaire should be administered face-to-face in clinic at 4 weeks, and not at the 5 week data collection point. A first resource use questionnaire administered in clinic will allow patients to interface with the research team to clarify any queries; check the questionnaire for missing data; and instruct patients on how to complete the second questionnaire at home at 10 weeks. Patients' lives (and their resource use) will be very different after their cast or boot is removed at the 4 week visit and this may affect their recollection of health care needs. In addition, including resource use questions at the 5 week time point (3-10 days post 4 week appointment), would increase patient burden and jeopardize completeness of the primary clinical outcome. We will later approximate, using statistical methods, cost assumptions for 3-10 day incremental cost period.

7.5. Adverse events

Serious adverse events will be collected from the point of randomisation at each data collection time point for the duration of the study. See section 11 (Assessment of safety) for details.

7.6. Patients' experiences

Patients' experiences of their treatment will be explored via telephone interviews conducted by the qualitative researcher in the team. See section 12.3 (Qualitative component) for details.

7.7. Mobilisation and adherence to exercise

Data will be collected to assess whether participants have adhered to instructions to complete exercises. Physiotherapists will make recommendations for participants to exercise and mobilise their ankle as often in a day as pain allows based on an

advice leaflet specific to their treatment allocation (recommended at least 3 times a day.) Compliance will be defined as once per day or more.

8. PARTICIPANT SELECTION

8.1. Inclusion Criteria

Patients must satisfy the following criteria to be enrolled in the study:

- Received surgery for fixation of unstable ankle fracture
- Provision of informed consent to participate.

8.2. Exclusion Criteria

Patients who meet any of the following criteria will be excluded from study participation:

- Under 16 years old (skeletal immature).
- Poor skin condition at operation site.
- Serious concomitant disease (e.g. stroke, osteoporosis, arthritis).
- Diabetic neuropathy/other sensory neuropathy (lack of sensation).
- Non-ambulatory prior to injury.
- Active leg ulceration.
- Patients who are unable to understand the study information or unable to complete the outcome questionnaires.
- Surgeon concerned about quality of fixation/integrity of wound.
- Fracture requiring further stabilisation in/around the ankle (e.g. syndesmosis).
- Open ankle fracture (bone broken through skin).
- Participant is a participant in other concurrent interventional research which may over-burden the participant or confound data collection.
- Concomitant injuries which will have a confounding effect on rehabilitation in the opinion of the investigator.

8.2.1. Justification of exclusion criteria

Patients with serious concomitant diseases or concomitant injury are excluded because they may have different treatment and rehabilitation options. Patients with sensory neuropathy are excluded as they may be prone to developing pressure ulcers caused by poorly-fitting plaster casts/boots. Patients who have suffered an open ankle fracture are excluded because they are at greater risk of developing infection.

8.3. Withdrawal criteria

Participants have the right to withdraw their participation in the study at any time without affecting the standard of care the patient receives. Clinicians may also advise patients to withdraw from the study should they acquire significant concomitant disease during the course of this treatment. Once withdrawn, the patient will be advised to discuss their further care plan with their consultant. Withdrawal will not adversely affect patients' care in any way.

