12. STATISTICS AND DATA ANALYSIS

12.1. Sample Size Calculation

The study is powered to detect a 10-point difference in ankle score since patient and public involvement indicated that walking without aids/getting back to work were the most important issues. A change from support with a stick/crutch to no support and a change to getting back to normal work/activities of daily life from simpler or part-time work are both associated with a 10-point change on the Olerud and Molander¹⁴ subjective scale (primary outcome).

An estimate of standard deviation of the ankle score six weeks post-surgery was derived from an audit of 18 patients having plaster casts at Poole Hospital. This figure of 21.9 is very similar in magnitude to those reported in the Cochrane review¹³. Based on an unpaired t-test with two groups of equal size, assuming 90% power, a two-sided 0.05 significance level, a standard deviation of 21.9 and a mean difference of 10 points between the plaster and boot groups, a total sample size of 204 (102 in each group) is required²¹. The study will over-recruit by 20%²² to allow for non-responders, or missing data, not to contribute data to the main analysis. However it is anticipated that the true percentage will be reduced by offering flexible methods of completion; either online, post or by phone. As the study progresses, the percentage with missing primary outcome data will be monitored and discussed at regular trial management group meetings and reductions/increases in over-recruitment will be made accordingly so that the target of 204 with completed data is met.

The study will aim to recruit 246 patients in total (123 in each group) over a 2 year recruitment period.

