12.2. Description of statistical methods

A detailed Statistical Analysis Plan will be developed and signed off by the Trial Steering Committee before any analyses commence. The anonymised data will be analysed by 'intention to treat' (i.e. patients will be analysed in the treatment arm they were randomised to, even if they received something else, or swapped treatments). The analysis and initial write-up will be blinded to the treatment groups and will report according to the Consolidated Standards of Reporting Trials²³⁻²⁴, including a participant flow chart. No imputation methods for missing data will be used for the main effectiveness analyses.

12.2.1. Baseline descriptives:

Baseline descriptive data on demographics (gender, age, marital status, whether living alone, highest educational level, employment status, driving status), fracture characteristics (fracture classification, pattern, complexity), BMI, Olerud and Molander ankle score pre-injury, and EQ-5D will be presented overall and for both groups separately. This will help with (a) assessment of external validity of the trial, and (b) to see whether the 2 groups were comparable at baseline (no significance tests will be conducted). The Olerud and Molander scale includes a question on activity compared to before injury. This would make this question confusing to complete at baseline, and so for baseline only this question has been dropped and

all participants will be given the maximum score of 20 for this question (i.e. the score for work and activities same as before injury).

12.2.2. Primary outcome:

The primary outcome is the Olerud and Molander¹⁴ ankle score (measured out of 100) five weeks post-baseline. Questionnaires that were not completed in the 3-10 day time window will be treated as missing data.

Multiple regression including study site, age and fracture complexity as a factor will be used to compare mean ankle score at five weeks post-baseline between the plaster and boot groups.

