(e) The effectiveness of the intervention may vary across different subgroups (strata) of patients (e.g. age and fracture complexity). Therefore for each outcome

supplementary statistical analyses are proposed in which it is tested whether there is a statistical interaction between age and treatment arm and between fracture complexity and treatment arm. It is however acknowledged that statistical power will be reduced for these significance tests and they will be considered to be exploratory. Age will be grouped as: under 65 years of age at the time of fracture and 65 + years.

(f) The main analysis will use an “intention to treat” approach. As a supplementary analysis two sets of “per protocol” analyses will also be conducted. In the first of these, patients will be analysed according to the method (boot or plaster) that they actually wore. If patients crossed over from one to the other during the 4 week period they will be excluded from the per protocol analysis. If patients didn’t wear the boot/plaster for the full 4 weeks they will be excluded. In the second analysis participants will additionally be excluded if they didn’t perform the exercises recommended. Thus if they performed the exercises less than once per day they will be excluded

(g) Data on primary outcome completed outside of the 3-10 day window will be included in the analysis

(h) The robustness of the results to missing data will be assessed by repeating the analysis incorporating the imputed values that will be derived as part of the economic analysis (see section 12.4)

The study will also compare the ten week Olerud and Molander Ankle score between groups to check whether any differences still remain at 10 weeks.

To see whether patients in both groups have returned to pre-injury levels of function we will calculate the mean difference (95% CI) between pre-injury and 10 week values for each group, and the proportion of patients whose score is worse by 10 points or more. These statistics will also be compared between groups.

12.2.3. Secondary outcomes:

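### Section 8.3 lets unblinded clinicians advise withdrawal from the whole study for disease acquired after randomisation, with no provision for continued follow-up, which exposes the intention-to-treat analysis to selective loss

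*Protocol*

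**What the plan says.** Section 8.3 first gives participants the usual right to withdraw at any time, and then adds a route started by the clinician: "Clinicians may also advise patients to withdraw from the study should they acquire significant concomitant disease during the course of this treatment". It does not define *significant*. On what follows, it speaks only of care: "Once withdrawn, the patient will be advised to discuss their further care plan with their consultant". It does not separate stopping the allocated treatment from leaving follow-up, and neither it nor any other section says that outcomes are still collected after such a withdrawal.

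Section 5.2 says that neither patients nor treating clinicians can be blinded.

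Section 12.2 defines intention to treat as follows: "patients will be analysed in the treatment arm they were randomised to, even if they received something else, or swapped treatments". It also says: "No imputation methods for missing data will be used for the main effectiveness analyses".

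The entry criteria in section 8.2 exclude a related group, "Serious concomitant disease (e.g. stroke, osteoporosis, arthritis"), and section 8.2.1 gives the reason: "Patients with serious concomitant diseases or concomitant injury are excluded because they may have different treatment and rehabilitation options".

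**The concern.** The analysis in section 12.2 needs a score from every randomised patient, including those whose treatment course changed. Section 8.3 works against this. It invites a clinician who knows the arm to suggest leaving the study, on a loosely worded criterion that arises after randomisation. Read naturally, the rule covers the four weeks of allocated treatment, so it acts before the 5-week ankle score is due.

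New significant disease is likely to go with poorer function and a different rehabilitation course; section 8.2.1 makes this point about serious disease at entry. The scores lost are therefore unlikely to be a random sample. If advice or uptake differed by arm, the arm losing more of these patients would look better than it is. An analysis plan cannot repair this afterwards, because the scores would not have been collected. What is at stake is how far the primary comparison can be trusted as a comparison of randomised groups.

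**Working it through.** **1. The plan's own figure.** Section 12.1 sizes the trial "assuming 90% power, a two-sided 0.05 significance level, a standard deviation of 21.9 and a mean difference of 10 points", and arrives at 102 per group.
- Normal approximation: n = 2 × (1.960 + 1.282)² × 21.9² / 10² ≈ 101 per arm.
- Exact t-test: 101 per arm gives 89.8% power and 102 gives 90.1%.

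The figure of 204 is reproduced and is not in dispute.

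**2. What happens to one participant.** A patient is randomised, acquires a disease the clinician judges significant, is advised to leave the study, and agrees before week 5.
- Section 8.3 describes no further data collection.
- There is no 5-week score, and section 12.2 imputes none in the main analysis.
- The patient is absent from the primary regression.

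Had the same patient only stopped or changed the boot or plaster, section 12.2 would have kept them in their randomised arm. The loss comes from the word *study* in section 8.3, not from the illness or the treatment change.

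**3. Size of the shift.** Suppose a fraction k of one arm is lost, with a mean g points below the rest of that arm. The full arm mean is M − k × g, where M is the mean of those who remain, and the observed mean is M. The arm is overstated by k × g. With losses in both arms, the difference shifts by k₁g₁ − k₂g₂. The protocol gives neither k nor g; the values below are assumptions, with all losses in one arm.

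| k (one arm only) | g = 10 | g = 20 | g = 30 |
|---|---|---|---|
| 1% | 0.1 | 0.2 | 0.3 |
| 5% | 0.5 | 1.0 | 1.5 |
| 8% | 0.8 | 1.6 | 2.4 |

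At k = 8% and g = 25 the shift is 0.08 × 25 = 2.0 points, so roughly 0.1 to 2 points describes the range, with 2.4 in the extreme corner. With equal k and g in both arms the shift is 0. For scale, the standard error of the difference at 102 per arm is 21.9 × √(2/102) = 3.07 points, so a 2-point shift is about 2/3.07 = 0.65 standard errors.

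**4. Effect on precision.** Assume a further 1% to 5% is lost on top of 20% missing for other reasons. The protocol gives two recruitment totals (246 in section 12.1, 276 in the synopsis; a separate matter), so both are shown.
- 246: 246 × 0.80 × 0.99 / 2 = 97.4 per arm, power 88.7%; with 0.95 in place of 0.99, 93.5 per arm, power 87.4%.
- 276: 109.3 per arm, power 91.9%; 104.9 per arm, power 90.8%.

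With 246, the 20% loss alone leaves 98.4 per arm, and 98 per arm already gives only 88.9%. The rule adds little to this. The issue is possible bias, not power.

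**5. Whether existing provisions cover it.**
- Over-recruitment by 20% and monitoring of missingness (section 12.1) restore numbers. They do not restore comparability if those lost differ from those kept.
- Sensitivity analysis (h) in section 12.2.2 says: "The robustness of the results to missing data will be assessed by repeating the analysis incorporating the imputed values". Those values come from the economic imputation in section 12.4, which uses baseline socio-demographics, cost categories and utilities. If loss depends on a new disease not recorded in those variables, imputation would not remove the bias.

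**The case against.** The strongest reply is that this is a permissive sentence with small consequences. Several parts of that reply stand, and they rule out stronger readings that a reader might infer.

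- *That section 8.3 re-applies the entry exclusion after randomisation.* It does not do so formally. Section 8.2 says *serious* and gives examples; section 8.3 says *significant*, gives none and does not refer to 8.2. No later eligibility check is described.
- *That clinicians remove patients.* They may advise; the patient decides.
- *That deep vein thrombosis, pulmonary embolism or wound infection trigger the rule, so that the arm with more of them sheds its worst results.* Sections 7.2.4, 10.3 and 11.2 class these as complications and report them as outcomes, and section 9.6.2 expects patients with complicated recoveries to return to clinic. If concomitant disease means unrelated illness, there is less reason to expect an imbalance. The undefined wording leaves room for another reading, but nothing states it.
- *That the safety comparison is lost.* Complications are drawn partly from hospital records and serious adverse events are followed to resolution (sections 7.2.4 and 11.4). Neither section says expressly that this continues after withdrawal, but neither relies on questionnaires alone.
- *That intention to treat cannot be delivered.* By the protocol's own definition it can be carried out on those with data, and some loss is planned for.

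The top of the assumed range is also demanding: 8% of 123 is about 10 patients in one arm and none in the other, before week 5, in a population screened for serious disease at entry.

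The reply does not remove the central point. The protocol sets out a route by which prognosis-related scores are lost, and nothing in it keeps these patients in follow-up.

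**Conclusion.** The point holds as a weakness in the withdrawal rule, well short of a fatal flaw. Section 8.3 does not separate decisions about treatment from participation in follow-up, and it lets unblinded clinicians advise study withdrawal on an undefined criterion arising after randomisation. With observed scores only in the main analysis, the intention-to-treat comparison is not protected against selective loss.

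Confidence in the reading of the text is high; confidence in the size is low. The range in step 3 depends on assumed loss rates, assumed score deficits and losses confined to one arm. It is probably small beside the 10-point target, and disappears if losses are similar in the two arms. The change is still worth making, because it costs little and the missing scores could not be recovered later.

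**What to change.** In section 8.3, replace the advice to withdraw from the study with a statement on data collection:

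- Clinical decisions about care or allocated treatment stay with the clinician and do not end study participation.
- The ankle score, EQ-5D-5L, resource use and complications continue to be collected, and are analysed as randomised, unless the participant withdraws consent to follow-up.
- Withdrawals and their reasons are recorded and reported by arm.

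The participant's own right to withdraw is unchanged, and the text should set no rule on managing the disease or on when the boot or plaster stops.

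The cost is a short amendment, a reminder to sites and a few more questionnaires from unwell participants. The 5-week and 10-week questionnaires are completed at home, so no visits are added. One detail to settle: section 9.5 counts the 5-week window from the 4-week appointment, so the amendment should say how the window is set for a participant who misses that appointment.
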